7.0 Vulnerable Populations

If the research involves special populations that are considered vulnerable, describe the safeguards included to protect their rights and welfare.

NOTE: You should refer to the appropriate checklists, referenced below, to ensure you have provided adequate detail regarding safeguards and protections. You do not, however, need to provide these checklists to the IRB.

7.1 *For research that involves **pregnant women**, safeguards include:*

NOTE CHECKLIST: Pregnant Women (HRP-412)

Response:

N/A: This research does not involve pregnant women.

7.2 *For research that involves **neonates of uncertain viability or non-viable neonates**, safeguards include:*

NOTE CHECKLISTS: Non-Viable Neonates (HRP-413), or Neonates of Uncertain Viability (HRP-414)

Response:

N/A: This research does not involve non-viable neonates or neonates of uncertain viability.

7.3 *For research that involves **prisoners**, safeguards include:*

NOTE CHECKLIST: Prisoners (HRP-415)

Response:

N/A: This research does not involve prisoners.

7.4 *For research that involves **persons who have not attained the legal age for consent to treatments or procedures involved in the research (“children”)**, safeguards include:*

NOTE CHECKLIST: Children (HRP-416)

Response:

N/A: This research does not involve persons who have not attained the legal age for consent to treatments or procedures (“children”).

7.5 *For research that involves **cognitively impaired adults**, safeguards include:*

NOTE CHECKLIST: Cognitively Impaired Adults (HRP-417)

Response:

N/A: This research does not involve cognitively impaired adults.

7.6 Consider if other specifically targeted populations such as students, employees of a specific firm, or educationally or economically disadvantaged persons are vulnerable. **Provide information regarding their safeguards and protections, including safeguards to eliminate coercion or undue influence.**

Response: N/A

8.0 Eligibility Screening

8.1 Describe screening procedures for determining subjects' eligibility.

Screening refers to determining if prospective participants meet inclusion and exclusion criteria.

Include all relevant screening documents with your submission (e.g. screening protocol, script, questionnaire).

Response:

All subjects will be recruited from the CEG-MS study. Subjects will undergo eligibility screening conducted by trained members of the research team using the attached phone and in-person script, and screening form to determine whether or not they are interested and meet all of the eligibility criteria outlined above.

Please see attached.

9.0 Recruitment Methods

N/A: This is a records review only, and subjects will not be recruited. NOTE: If you select this option, please make sure that all records review procedures and inclusion/exclusion screening are adequately described in other sections.

9.1 Describe when, where, and how potential subjects will be recruited.

NOTE: Recruitment refers to how you are identifying potential participants and introducing them to the study. Include specific methods you will use (e.g. searching charts for specific ICD code numbers, Research Participant Groups, posted advertisements, etc.).

Response:

Potential participants will be identified from the pre-existing list of study participants of the CEG-MS study database. Recruitment will be directed towards subjects who completed MRI evaluation for the CEG-MS study. These individuals will then be further screened based on the inclusion and exclusion criteria and contacted in person and via phone. If they are interested, the remaining screening questions will be asked. If the individual agrees to participate in the study, their appointment for testing will be scheduled based on their availability and convenience.

9.2 *Describe how you will protect the privacy interests of prospective subjects during the recruitment process.*

NOTE: Privacy refers to an individual's right to control access to him or herself.

Response:

Contact information from CEG-MS study databases is retained on a secure network in Buffalo Neuroimaging Analysis Centre (BNAC). The network is password protected and can only be accessed by PI and trained study members. Information is de-identified within the contact information file and only those with access to both that file and a separate de-identifying key file called 'CEG Codes' will be able to link the potential participant's name to his/her contact information. Once a participant has been recruited, his/her information will be removed from the recruitment contact information file.

9.3 *Identify any materials that will be used to recruit subjects.*

NOTE: Examples include scripts for telephone calls, in person announcements / presentations, email invitations.

 *For advertisements, include the final copy of printed advertisements with your submission. When advertisements are taped for broadcast, attach the final audio/video tape. NOTE: You may submit the wording of the advertisement prior to taping to ensure there will be no IRB-required revisions, provided the IRB also reviews and approves the final version.*

Response:

Please see attached phone and in-person script.

10.0 Procedures Involved

10.1 *Provide a description of **all research procedures or activities** being performed and when they are performed once a subject is screened and determined to be eligible. Provide as much detail as possible.*

NOTE: This should serve as a blueprint for your study and include enough detail so that another investigator could pick up your protocol and replicate the research. For studies that have multiple or complex visits or procedures, consider the addition of a schedule of events table in in your response.

Response:

The participant will be asked to make a total of two (2) visits, approximately 90 days apart. Each visit will involve: neuro-performance testing, and self-report questionnaires. Each study visit is expected to take approximately 1-2 hours. Between the two visits, the participant will be asked to complete a 12 week, computer-based cognitive training program. This includes 1 hour of training each day for 5 days each week.

On Visit 1, the participants will undergo a full battery of neuro-performance tasks including tests and questionnaires that measure your memory, thinking speed, fatigue, and personality. This visit is expected to take approximately 1-2 hours. The participants will be also asked to have a close friend or family member to complete similar surveys. A self-addressed envelope containing these questionnaires will be provided to take home with them. The participant will need to pass it onto a close friend or family member to be completed and mailed back.

In addition, the participant will be asked to take part in the 12 week computerized cognitive training program. This can be done at home, or anywhere the participant has access to a computer and internet. This cognitive training has been shown to improve cognitive performance in people with multiple sclerosis. The training involves a variety of interactive exercises which adapt to your abilities. The participants will need complete 1 hour of training each day, for 5 days each week.

At 90 days, the participant will return for the 1-2 hours' follow-up visit where they will complete the same cognitive testing and questionnaires which they had completed during visit 1.

All study visits will take place at Buffalo General Hospital. All of the procedures described above will be performed by a trained member of the research team as part of the research study.

If an individual is ineligible for participation, their screening information will be discarded (i.e., shredded). If participants are deemed eligible (either in person or over the phone), they will be scheduled to come in to the hospital for neuropsychological testing. Written consent will be obtained prior to administration of tests. As part of the consent process, participants will be asked for permission to use any data collected as part of the screening process as well.

10.2 Describe what data will be collected.

NOTE: For studies with multiple data collection points or long-term follow up, consider the addition of a schedule or table in your response.

Response: Demographic/social history, health history (as provided by participants during screening, review of medical records, etc.), and cognitive test data.

10.3 List any instruments or measurement tools used to collect data (e.g. questionnaire, interview guide, validated instrument, data collection form).

Include copies of these documents with your submission.

Response: Below is a list of neuropsychological tests that will be included. Symbol Digit Modalities Test (SDMT), California Verbal Learning Test 2nd Edition (CVLT), Brief Visuospatial Learning Test Revised (BVMT-R), Delis-Kaplan Executive Function System [DKEFS] Sorting Test, Delis-Kaplan

Executive Function System [DKEFS] Tower Test. Self-report/informant-report surveys have been uploaded. Self-report measures include the Beck Depression Inventory-Fast Screen (BDI-FS), Multiple Sclerosis Neuropsychological Questionnaire (MSNQ), Fatigue Severity Scale (FSS), NEO-FFI personality inventory, Multiple Sclerosis Quality of Life (MSQoL) and Elithorn's Perceptual Maze Test (EPMT). Informant-report measures include the NEO-FFI.

10.4 Describe any source records that will be used to collect data about subjects (e.g. school records, electronic medical records).

Response: We will be collecting MRI and EDSS information for subjects from the database of IRB no. 603069 of CEG- MS study.

*10.5 Indicate whether or not **individual** subject results, such as results of investigational diagnostic tests, genetic tests, or incidental findings will be shared with subjects or others (e.g., the subject's primary care physician) and if so, describe how these will be shared.*

Response: In case of any incidental findings, the details will be shared with subject's primary care physician by adhering to the procedures and reporting policies as outlined by the UBIRB. Results will not be shared with participants or anyone else. Any incidental findings for the patients will be relayed to the primary neurologist who can make the determination regarding whether to share this information with the participant's primary care physician.

*10.6 Indicate whether or not **study** results will be shared with subjects or others, and if so, describe how these will be shared.*

Response: Study results will not be shared with subjects.

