2.0 Scientific Endpoints

2.1 Describe the scientific endpoint(s), the main result or occurrence under study.

*NOTE: Scientific endpoints are outcomes defined before the study begins to determine whether the objectives of the study have been met and to draw conclusions from the data. Include primary and secondary endpoints. Some example endpoints are: reduction of symptoms, improvement in quality of life, or survival. Your response should **not** be a date.*

Response: Our primary end-point are predictive. Our first primary end-point will have been met if baseline measures of personality, as measured by the NEO-Five Factor Inventory (NEO-FFI), will predict overall cognitive improvement following rehabilitation. Likewise, our second primary end-point will have been met if baseline measures of brain connectivity predict specific improvements in cognitive sub-domains, following rehabilitation. Cognitive improvement will be measured according to changes from visit 1 to visit 2 for the following neuropsychological tests: Symbol Digit Modalities Test (SDMT), California Verbal Learning Test 2nd Edition (CVLT), Brief Visuospatial Learning Test Revised (BVMT-R), MS Neuropsychological Screening Questionnaire (MSNQ), Delis-Kaplan Executive Function System (DKEFS) Sorting Test, Tower of London (TOL), Elithorn's Perceptual Maze Test (EPMT).

	Day 0 (Visit 1)	Day 90 (Visit 2)
NEO Five Factor Inventory (NEO-FFI)	X	X
Symbol Digit Modalities Test (SDMT)	X	X
California Verbal Learning Test Second Edition (CVLT)	X	X
Brief Visuospatial Memory Test Revised (BVMT)	X	X
MS Neuropsychological Screening Questionnaire (MSNQ)	X	X
Delis Kaplan Executive Function System Tower Test (DKEFS-TT)	X	X
Delis Kaplan Executive Function System Sorting Test (DKEFS-ST)	X	X
Elithorn's Perceptual Maze Test (EPMT)	X	X
Multiple Sclerosis Quality of Life (MSQoL)	X	X
Beck Depression Inventory Fast Screen (BDI-FS)	X	X
Fatigue Severity Scale (FSS)	X	X

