In order to address our second goal, we will use a multi-parametric approach in which we account for cerebral pathology, such as regional gray matter atrophy, microstructural white matter damage, lesion volume and localization, white matter tract integrity and structural connectivity, and resting state functional connectivity. We will apply network-based analysis, where appropriate, in order to account for network-level organization of the brain. These methods of analysis are well-suited for elucidating patterns of insult which lead to changes in complex emergent phenomenon such as higher level cognition.

Our results may provide foundation for better directing rehabilitation and behavioral treatments. For instance, a short questionnaire could be used to identify patients whose personality profile puts them at greater risk for unfavorable disease progression. An understanding of this risk could help direct efforts which mitigate against these unfavorable outcomes. Similarly, baseline patterns of cerebral pathology could also be employed to predict responses to the cognitive and other behavioral interventions. There is a burgeoning interest in personality trait adaptation and personalized health plans among health care agencies²² and we believe our research will contribute meaningfully to this growing field of interest.

3.2 Include complete citations or references.

Response:

2. McCrae RR. Trait psychology and culture: exploring intercultural comparisons. *J Pers*. 2001;69(6):819-846.
doi:10.1037/0022-3514.52.1.81.

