4.0 Study Design

4.1 *Describe and explain the study design (e.g. case-control, cross-sectional, ethnographic, experimental, interventional, longitudinal, observational).*

Response: Interventional

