5.0 Local Number of Subjects

5.1 *Indicate the total number of subjects that will be enrolled or records that will be reviewed locally.*

Response: We will recruit 50 subjects with multiple sclerosis who are already enrolled in CEG-MS study.

5.2 *If applicable, indicate how many subjects you expect to screen to reach your target sample (i.e. your screen failure rate).*

Response:

We expect that potential participants to be enrolled through the CEG-MS study for suitability for the study. Subjects who agree to participate and pass screening requirements will be enrolled in the study.

5.3 Justify the feasibility of recruiting the proposed number of eligible subjects within the anticipated recruitment period. For example, how many potential subjects do you have access to? What percentage of those potential subjects do you need to recruit?

Response: This research will be conducted through the Buffalo Neuroimaging Analysis Center (BNAC) group. We expect to recruit subjects from the CEG-MS study database. Based on our targeted population, we believe there is a sufficient number of potential participants to meet participant target of 50 in adherence to the protocol.

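### With one trained group tested twice, the plan can show what predicts 90-day cognitive change but not what predicts response to rehabilitation, and several of its aims claim the latter

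*Protocol*

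**What the plan says.** Protocol 4.1 describes the design in one word ("Response: Interventional"). Section 5.1 gives the whole sample: "We will recruit 50 subjects with multiple sclerosis who are already enrolled in CEG-MS study". Under 10.1, "The participant will be asked to make a total of two (2) visits, approximately 90 days apart", and between the visits "the participant will be asked to complete a 12 week, computer-based cognitive training program". At the second visit "they will complete the same cognitive testing and questionnaires which they had completed during visit 1".

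The outcome is the difference between the two visits. Section 2.1 states: "Cognitive improvement will be measured according to changes from visit 1 to visit 2 for the following neuropsychological tests", and then lists seven measures. Protocol 17.1 and the SAP convert the scores to z-scores, average them, and regress the change on baseline Conscientiousness (aim 1a). They add interaction terms for executive function and adherence (aim 1b) and use statistical learning on connectome features (aim 2).

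The claims drawn from this differ in strength:

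- Section 2.1 says that baseline personality "will predict overall cognitive improvement following rehabilitation". This is a statement about prediction and time order.
- Sections 1.1 and 1.2 speak of the trait's impact on rehabilitation, and of connectome differences explaining how participants respond to it.
- Section 17.1 and the SAP frame aim 1a as whether Conscientiousness forecasts that the intervention succeeds.
- Section 3.1 looks ahead to use: "Our results may provide foundation for better directing rehabilitation and behavioral treatments".

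**The concern.** Each person's change is the sum of at least three parts: the effect of training, the gain from having met the tests before, and whatever would have happened over 90 days anyway. With every participant trained and only two assessments, nothing in the data separates these parts.

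A retest gain that is equal for everyone shifts the mean and leaves the regression slope alone. The difficulty arises only if the gain differs between people in a way related to the predictor. The plan's own background makes that plausible: section 3.1 describes Conscientiousness in terms of striving, organization and deliberation, and reports that lower scores go with slower processing speed. Executive function and connectome measures are also close to the ability to learn from a first exposure.

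At stake is the interpretation of a positive result. It could be reported as showing who benefits from rehabilitation, and used to direct it, when it shows only who improves on retesting. A larger sample would not help, because the problem is identification and not precision.

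**Working it through.** **The plan's own figure.** Protocol 17.2 gives 41 participants for 80% power at an effect size of 0.38. The metric, alpha and sidedness are not stated. Read as a correlation, with Fisher's z, n = ((z_alpha + z_power)/atanh(0.38))² + 3:

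- one-sided 5%: ((1.645 + 0.842)/0.400)² + 3 = 41.6, so 41 is reproduced to within rounding;
- two-sided 5%: ((1.960 + 0.842)/0.400)² + 3 = 52.0, so 41 is not reproduced.

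This concerns power to detect a correlation with change. It does not bear on what that correlation means.

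**How far practice alone could carry the result.** Inputs from the documents: n = 50 (5.1) and seven measures in the composite (2.1). Everything else is assumed, because the documents give no values and this design cannot estimate them: reliability 0.8 per test, independent errors, training-response SD 0.2 in z units and unrelated to Conscientiousness, practice-gain SD (SDp) 0.1 to 0.3, and correlation of practice gain with Conscientiousness (rho) 0 to 0.5.

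1. Error SD of the composite change = sqrt(2 × (1 − 0.8)/7) = sqrt(0.4/7) = 0.239.
2. SD of total change = sqrt(0.239² + 0.2² + SDp²) = 0.327, 0.370 and 0.433 for SDp = 0.1, 0.2 and 0.3.
3. Induced correlation r = rho × SDp / SD of total change. For example, rho = 0.3 and SDp = 0.2 give 0.3 × 0.2/0.370 = 0.162.
4. Two-sided 5% rejection rate at n = 50 from Fisher's z, with mean atanh(r) × sqrt(47) and critical value 1.96. For r = 0.162 the mean is 1.12 and the rate is 20%.

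| rho | SDp 0.1 | SDp 0.2 | SDp 0.3 |
|---|---|---|---|
| 0 | 5% | 5% | 5% |
| 0.1 | 5.5% (r = 0.03) | 7% (0.05) | 8% (0.07) |
| 0.2 | 7% (0.06) | 12% (0.11) | 16% (0.14) |
| 0.3 | 10% (0.09) | 20% (0.16) | 30% (0.21) |
| 0.5 | 18% (0.15) | 48% (0.27) | 70% (0.35) |

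**Cross-check by simulation.** With 20,000 replicates at n = 50, practice was set to a share s of the variance in change, so the expected correlation is rho × sqrt(s). Two-sided rejection was 11% (rho 0.20, s 0.25), 16% (0.20, 0.50), 27% (0.38, 0.25) and 48% (0.38, 0.50). It stayed at 5% with rho = 0. The two calculations agree in pattern.

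**The case against.** The strongest reply is that 2.1 never promises more than prediction. It calls the end-points predictive, and improvement after rehabilitation is a matter of time order. A reader might infer that meeting 2.1 through practice gain would be a false positive. The documents do not support that: if baseline measures predict 90-day change, the end-point as written is truly met. This stands. The overreach lies in 1.1, 1.2, 17.1 and the SAP.

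A reader might also infer from 10.1 that identical forms are reused. The phrase may mean only the same battery, as in the schedule in 2.1, and the instruments submitted with the application are not available here. What can be said is that the forms are unstated, although 10.1 asks for enough detail to replicate the study.

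The size is open to challenge too. Every influential input is assumed, and the highest rates need a correlation of 0.5, above the 0.38 that 17.2 plans on for training success itself. The MSNQ, one of the seven measures, is a questionnaire to which item practice hardly applies, which would lower the figures somewhat. The direction is not fixed either: people with lower Conscientiousness may have more room to gain, and higher scorers may meet ceilings, which would weaken or reverse the slope. All of this stands, so no single rate should be quoted as the plan's error rate.

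Two other replies carry less weight. The adherence interaction in aim 1b does give some information, since a pure practice association should not depend on training dose. But dose is not randomised, and 3.1 itself expects adherence to depend on Conscientiousness. Section 10.1 also says the training is already known to improve cognition in MS, but an average effect does not show who responds.

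**Conclusion.** The concern holds in a limited form. The study can answer whether baseline Conscientiousness or connectome measures predict 90-day cognitive change in people who undertook training. It cannot show that they predict response to the training, and the aims, hypotheses, 17.1 and SAP should not say so.

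The numerical consequence is unknown. Under the stated assumptions, the chance of a significant slope with no link to training response runs from about 5.5% to 70% at n = 50, and is 5% if practice gain is unrelated to the trait. That range shows the issue could be negligible or serious; it does not show which.

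A reader might infer that the study needs a control arm. That does not follow for a prediction study of this size. For illustration, to distinguish a correlation of 0.38 in trained participants from 0 in untrained ones with 80% power, the number per arm is 2 × ((z_alpha + z_power)/atanh(0.38))² + 3. This gives 81 per arm (162 in all) one-sided, or 102 per arm (204 in all) two-sided. Narrowing the claim is the proportionate course.

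**What to change.** 1. **Wording, the essential change.** In Protocol 1.1, 1.2, 2.1 and 17.1 and in the SAP, restate the aims and conclusions consistently as predicting 90-day cognitive change in people with MS who undertook the training. Add one sentence saying that prediction of response to rehabilitation is not identified without an untrained comparison, and that the adherence interaction is a non-randomised dose contrast. All these places need the change together, or the documents will disagree with one another. The cost is wording and a narrower claim.

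2. **Test forms.** In 10.1, state which form of each test is given at each visit. For tests that have alternate forms (which ones do is an assumption, as the documents do not say), give the alternate at visit 2, counterbalance the order across participants, and include form order in the regression. The cost is the extra record forms, an order list, a model term and slight noise from form differences. This reduces item-specific practice but does not remove task familiarity or natural change, so it supplements the first change and cannot replace it.
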